21.1. Compensation for Research-Related Injury: N/A

21.2. Contract Language: N/A

22. Consent Process

22.1. Consent Process (when consent will be obtained): Our consent process is informed by the instructions provided in HRP-090 and HRP-091. The consent process will take place on site at NUWAY (for electronic administration, it will take place via Zoom). Research staff will meet with prospective participants. First, participants will complete a screening informed consent document then they will be screened using our screening document (attached to ETHOS). If the participant meets eligibility, we will offer the participant the choice of reading the informed consent document and we will verbally summarize it for them in detail. Participants will be administered the UBACC quiz to determine that they have understood the study and their role in the study. A score of 15 or higher is needed for inclusion in the study. An impartial witness will be used if necessary, for example, if the prospective participant has a visual impairment and cannot read the informed consent document. If an impartial witness is used we will follow the guidelines described in HRP-090 for that procedure.

22.2. Waiver or Alteration of Consent Process (when consent will not be obtained, required information will not be disclosed, or the research involves deception): N/A

22.3. Non-English Speaking Participants: N/A

22.4. Participants Who Are Not Yet Adults (infants, children, teenagers under 18 years of age): N/A

22.5. Cognitively Impaired Adults, or adults with fluctuating or diminished capacity to consent: N/A

22.6. Adults Unable to Consent:

- Permission: N/A
- Assent: N/A

23. Setting

23.1 Research Site: **NUWAY House, Inc.** NUWAY is the host partner for the proposed study. NUWAY is a private, not-for-profit substance-use disorder treatment facility serving men and women with addictions since 1966. NUWAY operates five treatment centers which serve over 700 clients in the Twin Cities. The proposed work will recruit from NUWAY's 3R's Counseling Center, [name] which currently serves 288 intensive outpatient clients for individualized treatment durations generally ranging from 90-120 days. This is a 17,000 square foot facility featuring 13 group rooms, 21 offices assigned to counseling staff, eight therapy offices with standard office furniture that are open to any staff member or clinician for client interviewing (which we have been permitted to use to screen and consent clients), several client lounges, a cafeteria for clients, a lecture hall that seats 150 people, a smoking area, and an outdoor green space. There is high-speed wireless internet throughout the facility that can be accessed by research staff and clients to upload their journals and complete daily assessments. 3R's has 18 full-time licensed clinicians, two program managers, one program director, four admissions staff, 14 interns from various counseling programs throughout the Twin Cities, and 7 floating therapists who fill in as needed. Clients at 3R's receive 20 hours of licensed substance-use disorder treatment per week, 4 hours per day, Monday through Friday. Treatment elements include educational lectures, process group therapy, and individual therapy. PPJ is not redundant with current services offered. The facility is 4.5 miles from the PI's office at the School of Social Work, a 13 minute drive. During COVID19, NUWAY staff are providing groups and individual sessions to clients on Zoom.

As of August 2020, we will also be recruiting from a second NUWAY site, "NUWAY III." NUWAY III is located at [name]. NUWAY III is a medium-intensity residential treatment program for women and transgender people. The program provides comprehensive treatment for substance use and mental health disorders and has the capacity for 31 women and transgender people. NUWAY III offers gender-informed curriculum, treats trauma, and offers individual and group therapy.

As of September 2020, we will also be recruiting from a third NUWAY site, "2118." Nuway's [name] location in Minneapolis, MN, serves over 220 outpatients each year. Nuway is an extended care outpatient facility where clients attend treatment 4 hours per day, Monday through Friday, for 90-120 days. "2118" is a 20,000 square foot facility featuring 10 group rooms, 16 offices assigned to counseling staff, five therapy offices, several client lounges including five designated as quiet

areas, a cafeteria for clients, a lecture hall that seats 135 people, a smoking area, and an outdoor green space. “2118” has 15 full-time licensed clinicians, two clinical supervisors, one program director, one executive program director, three admissions staff, three information technology support staff, 6-10 interns from various counseling programs throughout the Twin Cities, and 2-4 floating therapists who fill in as needed.

All study procedures are the same for all NUWAY sites.

2. International Research: N/A
3. Community Based Participatory Research: N/A

2. Multi-Site Research

N/A

3. Resources Available

3.2. Resources Available:

Time. The Agricultural Experiment Station (AES) grant that is funding this study provides PI [name] with one course buy out for the academic year 2019-2020. PI [name] will use this time and additional time to conducting and completing this research.

Research Assistant(s) (RA). The AES grant that is funding this study allows for two 25% RAs for the 2019-2020 school year and two 25% RAs for the 2020-2022 school year. One RA will be dedicated to this study. The CTSI grant will also provide a second RA. The RAs will be involved in all aspects of the research including screening and informed consent, data management, data cleaning, literature reviews, exit interviews, attending group sessions, and general research activities.

Facilities. The School of Social Work is home to five research and training centers that serve local and national educators, researchers, and professional social workers. The School is located at [name]. Faculty members at the School of Social Work are among the most productive in the nation, conducting research on a wide range of topics. The School produces a wide range of high-quality research relevant to social welfare including work in health, mental health, disability, aging, and methods and methodology (<http://www.cehd.umn.edu/ssw>). The School of Social Work’s research committee hosts monthly research

colloquia to showcase the current research of University of Minnesota faculty.

Offices. A 118 square foot office for PI [name] is permanently available in Peters Hall. The office features a desk, credenza, attached table with two guest chairs, two lockable large two-drawer filing cabinets, one lockable three-drawer filing cabinet, and high-speed internet access hardwired to a laptop docking station. The University's wireless network is also accessible throughout Peters Hall. Project staff will be equipped with additional office space in Peters Hall similarly equipped with desks, chairs, filing cabinets, computers, and internet service. During COVID19 [name] is working remotely.

Computers. The PI has a Dell PC laptop (Windows 10) and two monitors. All research staff will have Dell PC workstations in their offices. The University provides SPSS Statistics Software and the PI has perpetual licenses for two copies of NVivo software for qualitative data analysis. Annual NVivo licenses have been purchased for additional research staff members.

Availability of medical or psychological resources. These currently exist at NUWAY and will be utilized if necessary via referral of the participant to NUWAY staff in the event of medical or psychological concerns beyond the scope of this study.

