The Treatment Group's Group Phase. Participants will meet for 8 hours of group content 2-3 times per week for 3 weeks to learn PPJ. For electronic administration, these groups take place via Zoom.

PI [name] or another trained research staff member will conduct these intervention therapy groups. The primary aim of the groups is to teach the elements of PPJ. Groups and other Zoom meetings will be audio recorded or Zoom's instant audio transcription tool will be used to aid treatment manual development and to collect qualitative data. Zoom meetings will be video recorded (this happens automatically in Zoom), but client images will be edited out so as to completely remove them from the video recordings. These videos will be used by research staff to learn how to lead the treatment groups. The videos will include the audio track and only images of our PowerPoint slides and research study staff images. PPJ is taught by a counselor or group facilitator who themselves uses PPJ on a daily or near daily basis and the facilitator will practice PPJ along with participants in the group setting.

A NUWAY Inc. staff member will sit in on all group sessions. Study staff (research assistants) may also sit in on group sessions and may lead group sessions in the unlikely event of any absence of the primary group leader. [name], primary investigator, would provide supervision and instruction in such an event. NUWAY Inc. staff or research staff will also practice PPJ. Journals will be provided by the study to the study participants. For electronic administration, journals will be mailed or delivered to the participants and to the NUWAY staff member. A set of journals will also be delivered to the NUWAY office as a backup. Clients can pick up a journal on a usual face-to-face visit to NUWAY for drug screening. Journals will have pre-printed category headings listed on the pages (see the figure, above) and other PPJ elements such as note pages, worksheets for describing values and instructions for teaching PPJ to others. The study

PROTOCOL TITLE: Journaling and Addiction Recovery

VERSION DATE: 13 April 2021

will provide lap desks for participants to use to lean on when writing their journal entries unless we use a room with a table to lean on (this is not relevant to electronic administration). One additional journal will be provided if the original journal is lost or stolen during the group sessions.

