Participants will complete PPJ during group and will be invited to share some aspects of PPJ in a group process that will include modeling and coaching to support learning. During the sharing part of group, the facilitator and the NUWAY staff member and the Research Assistant will also (judiciously) share their own PPJ entries. In between group sessions, participants will be given homework to continue to practice and therefore learn the elements of PPJ. Group participants are also encouraged to share journal content judiciously as some content may feel private. Group participants are also encouraged to protect their privacy by writing some journal items using brief words, codes, or initials that would not be meaningful to another person.

See Table 1 below for a detailed plan for each group session.

Table 1. PPJ Treatment Group's Group Phase Daily Session Content. *Please note: this represents a general idea of content for each session. We will follow this general plan but the details (activities, PowerPoint slides, topics, exercises) might be modified week by week. Preparation of detailed group session plans, handouts and PowerPoint slides (if used) might be conducted the day before or the morning of group sessions. Therefore, there would not be time to gain approval for these details from the IRB in advance of the group session. However, we will submit detailed group session plans, PowerPoints and handouts to the IRB as soon as they are ready and we are able to submit them in a modification to the study.*

Please note: some of these sessions might be conflated based on host setting, for example, we might cover content of sessions 1 and 2 in a 2-hour session versus 2 1-hour sessions.

Exactly what is covered in each session may vary based on pacing of different groups but this sequence will be followed approximately.

Week and Session #	Session Content
--------------------	-----------------

PROTOCOL TITLE: Journaling and Addiction Recovery

VERSION DATE: 13 April 2021

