Open ended questions: Experience with 10 th step, journaling, gratitude practices, and using a planner.	4 minutes	Verbally administered using REDCap			Verbally administered using REDCap	Verbally administered using REDCap
What have you already heard about the study?	1 minute	Verbally administered using REDCap				
Hypothesized Mediators						
Positive and Negative Affect Schedule, including three items comprising the serenity subscale	2 minutes	X	X	X	X	X
Abstinence Self Efficacy Question (single item)	1 minute	X	X	X	X	X
Commitment to Sobriety (single item)	2 minutes		X	X	X	X
Alcohol craving (single item)	½ minute	X	X	X	X	X
Drug craving (single item)	½ minute	X	X	X	X	X
Happiness with Recovery (single item)	½ minute	X	X	X	X	X

PROTOCOL TITLE: Journaling and Addiction Recovery

VERSION DATE: 13 April 2021

Individual items to assess specific impact of PPJ journaling practice ¹ (attached as "single items to assess change")	3 minutes	X	X	X	X	X
Satisfaction with Life	1 minute	X	X	X	X	X
Quality of life scale, modified to compare quality of life during recovery ("now") to quality of life during active addiction ("then") ¹	3 minutes	X	Global quality of life item only	X	X	X
Flourishing scale	2 minutes	X		X	X	X
Treatment Group Only						
# of Qualtrics surveys completed				X	X	X
Ease, helpfulness, satisfaction, effort of PPJ (for control group, ease, helpfulness, satisfaction, effort of filling out the survey questionnaires)	2 minutes		X	X	X	
# group sessions attended				X		
# homework assignments completed				X		
# journal entries completed				X	X	
Count of # of items entered into PPJ		X	X	X	X	
Eligibility rate and consent rate (treatment and control group)						X
On approximately the fourth session of group (halfway through the total # of sessions) ask: "what is working for me in this journaling group is...." And "what is not working for me in this journaling group is...."						
Open Ended Survey Question						
Treatment group: What are your thoughts about Positive Peer Journaling (PPJ) so far?	2 minutes			X	X	
Outcomes						
Recurrence of Substance Use				X	X	X
Treatment Retention at NUWAY (successfully exiting treatment with staff approval versus against staff advice or at staff request)				X	X	X
Qualitative Exit Interview	45 minutes					X
1 month follow up interview	25 minutes					X

Baseline characteristics.

- Sociodemographics

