If participants leave NUWAY on good terms during the study period, they may still be able to continue to be in the study because it is possible to continue study activities from outside of NUWAY for the independent practice phase. Any smartphone or tablet can be used to continue to participate in the independent practice phase. We may reach out to participants who continue to participant in this way to encourage them to continue in the study or ask if they wish to remain in the study using the contact information they provide to use through NUWAY Inc.

Follow up Interview: At approximately 30 days after the exit interview, we will follow up with participants. Zoom is the first choice but a telephone interview is acceptable for this procedure. We will ask participants about any substance use and journaling in the past 30 days. We will ask a few additional qualitative questions such as what was most memorable about being in the research study, and other similar questions. Participants will be encouraged to complete their final Qualtrics survey before this interview.

- 5.4. Individually Identifiable Health Information: Research study staff will meet with NUWAY staff at reasonable intervals to collect data on our primary outcomes: 1) treatment retention and 2) recurrence of substance use. At these occasions we will go through our list of study participants and ask NUWAY staff if: 1) that person has left treatment or been asked to leave; 2) that person has had a positive urine analysis screening indicating recurrence of substance use. We will mark down the replies in our deidentified data file. If the participant cannot remember date of entry into NUWAY, we will also gain this information from NUWAY staff and the treatment record. To facilitate this work, study staff will use a password-protected file linking participants' real names with study IDs (codenames/numbers).

6. This study therefore includes PHI and therefore we have combined our informed consent document with the appropriate text from a HIPAA authorization form.

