17.2. Power Analysis: Preliminary data from existing behavioral activation (BA) research was used to determine power for the original proposal with N=76. For the outcome of abstinence (yes/no), previous work found outcomes for this variable of 41.5% for the BA group and 24.8% in the control group.¹⁴ For a 1-tailed test with $p < .10$, our power to detect a significant effect for abstinence (yes/no) in the proposed study would be .61 (for a 2-tailed test with $p < .05$, power would be .34). For the outcome of treatment retention (yes/no), previous work showed 96.6% for the BA group and 75.9% in the control group.¹⁶ For a 1-tailed test with $p < .10$, our power to detect a significant effect for treatment retention (yes/no) in the current study would be 94% (for a 2-tailed test with $p < .05$, power would be .82). Therefore, we should be adequately powered to detect statistically significant differences for the outcome of treatment retention in the current study using a 2-tailed test. R was used to conduct these power analyses.⁶¹

17.3. Statistical Analysis: This pilot study will not be adequately powered to detect an effect. Still we will compare the treatment and control groups using t tests and multi-level models to determine differences in means and in slopes between the groups, respectively. Descriptive statistics of the quantitative measures will be used to conduct power analyses and sample size calculations for a larger controlled trial. Also, multi-level analyses will

be conducted to determine significant change over time in factors of interest. We will also be able to examine whether change over time varied by certain subgroups (e.g., those with lower versus higher levels of the factor of interest at baseline).

17.4. Data Integrity: The use of Qualtrics to collect survey data will improve data accuracy because this allows us to avoid keystroke and other errors involved with manual data entry from written questionnaires. We will scrutinize the data produced by Qualtrics to ensure its integrity; whether values are within scale ranges and whether missing data is coded correctly. We will carefully examine and clean the data to ensure accuracy. For standardized instruments, we will be very careful to follow the directions for summing or taking the mean of scale items and reverse code any items as per the instructions.

18. Confidentiality

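### Staff who may attend or lead PPJ groups also record and clean the NUWAY-record outcomes, with arm not withheld and a question that does not match the outcome definitions

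*Combined protocol and SAP*

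**What the plan says.** **Roles.** Resources Available gives the research assistants overlapping duties: "The RAs will be involved in all aspects of the research including screening and informed consent, data management, data cleaning, literature reviews, exit interviews, attending" (the list then names the PPJ groups). The paragraph on trained research staff in the same section repeats the data cleaning and data management role. There are two assistants: "One RA will be dedicated to this study. The CTSI grant will also provide a second RA". The posts paid by the AES grant are 25% posts.

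**Part in delivering PPJ.** Section 5.2 (Group Phase) says: "Study staff (research assistants) may also sit in on group sessions and may lead group sessions in the unlikely event of any absence". When entries are shared in group, "the facilitator and the NUWAY staff member and the Research Assistant will also (judiciously) share their own PPJ entries".

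**Outcome capture.** Section 3.1 counts substance use and treatment retention among the primary outcomes. Section 5.2 (Outcomes) takes both from the NUWAY treatment record. Research staff cannot open that record. A NUWAY staff member reports from it, and research staff enter the information using the key that links names to codenames. Section 5.4 gives the question: "At these occasions we will go through our list of study participants and ask NUWAY staff if: 1) that person has left treatment or been" (this item closes with a request by NUWAY to leave). The second item is whether there was a positive urine screen.

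**Definitions.** Table 2 defines retention as "successfully exiting treatment with staff approval versus against staff advice or at staff request". Section 13.1 adds leaving without discussion and codes it, with the two adverse exits, as discontinued. For recurrence, 5.2 and 20.2 count urine tests, other drug screens and client self-report.

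**Cleaning.** Section 17.4 says: "We will carefully examine and clean the data to ensure accuracy". It does not say by whom, or whether arm is visible.

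**The concern.** Two things meet here. Anyone who sat in a cohort's PPJ groups knows who was in that arm, and holding the key undoes the de-identification of the file for that person. The question they are to ask also does not return the outcome as defined, so a reply has to be interpreted before it can be coded. Interpretation by someone who helped deliver one arm is a recognised route for bias, and most of it can be closed by procedure.

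What is at stake is mainly retention. Section 17.2 singles it out as the outcome with adequate two-tailed power, so readers are likely to treat it as a test even though this is a pilot. Section 17.3 also plans to use the quantitative results to size a larger trial.

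**Working it through.** **Step 1. Does the question return the defined outcome?**

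| Outcome | Definition | What the 5.4 question returns | Gap |
|---|---|---|---|
| Retention | Table 2: approved exit v against advice or at staff request; 13.1: left without discussion = discontinued | Left, or asked to leave | A reply that someone left does not separate approved exit, exit against advice and exit without discussion |
| Recurrence | 5.2 and 20.2: urine, other drug screens, self-report | Positive urine screen | Other screens and self-report are not asked about |

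The rule for each exit type exists once Table 2 and 13.1 are read together. What is missing is a question that returns the type.

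**Step 2. Is arm withheld anywhere?** I found no passage that masks outcome coders, data cleaners or analysts. No passage says that the coder sees the arm either; that is an inference from the roles and the key.

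**Step 3. The plan's own figures.** Inputs from 17.2: retention 96.6% v 75.9%, N = 76, taken as 38 per arm (1:1 is an assumption). With h = 2·asin√.966 − 2·asin√.759 = 0.655, power = Φ(h·√(38/2) − z):
- two-tailed .05: Φ(2.857 − 1.960) = .815 (stated .82)
- one-tailed .10: Φ(2.857 − 1.282) = .942 (stated 94%)

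Both reproduce.

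**Step 4. How many exits would matter?** Projected retained counts are .966 × 38 = 36.7 and .759 × 38 = 28.8, so 37 v 29. Section 11.1 now aims for about 100; with 50 per arm, .966 × 50 = 48.3 and .759 × 50 = 38.0, so 48 v 38. The table gives two-sided Fisher exact p after moving exits against PPJ. Fisher is my choice, since the plan names no test for yes/no outcomes.

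| Exits changed | 38 per arm | p | 50 per arm | p |
|---|---|---|---|---|
| None | 37 v 29 | .014 | 48 v 38 | .008 |
| One control | 37 v 30 | .028 | 48 v 39 | .015 |
| One PPJ | 36 v 29 | .047 | 47 v 38 | .023 |
| One in each arm | 36 v 30 | .086 | 47 v 39 | .041 |
| Two control | 37 v 31 | .056 | 48 v 40 | .028 |
| Two PPJ | 35 v 29 | .113 | 46 v 38 | .054 |
| Two in each arm | 35 v 31 | .309 | 46 v 40 | .148 |

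**Step 5. The reverse case.** Suppose true retention is 75.9% in both arms and a share m of PPJ exits is recorded as retained, so the recorded PPJ rate is .759 + m × .241. The chance of a false result favouring PPJ (pooled z-test, two-sided .05) is:

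| m | 38 per arm | 50 per arm |
|---|---|---|
| 0 | .025 | .025 |
| 10% | .044 | .048 |
| 20% | .073 | .085 |

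At 50 per arm, m = 20% is 50 × .241 × .2 = 2.4 exits. The values of m are assumptions; the documents give none.

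**The case against.** The strongest reply is that research staff mostly transcribe. NUWAY classifies the exit and holds the test results, 5.4 says that replies are marked down, and 5.2 lists NUWAY's reason for leaving among the data to be collected. A positive urine result leaves little to decide, and survey answers go straight into Qualtrics, so cleaning them involves little discretion. This stands in large part and keeps the point small. It does not close the gap in step 1: the reason for leaving is listed, but the 5.4 question does not ask for it.

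The second reply is that masking an assistant leaves the main route open. Under 5.2, counselors are told of group attendance and of control-arm survey participation. Under 18.1, NUWAY notes PPJ participation in the chart. An assistant who stays out of the groups may still learn the arm by randomising participants at screening (9.3, 12.1), reviewing journal photographs (19.2) or holding exit interviews (5.2). All of this stands.

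The third is that this is a pilot for feasibility and acceptability, which 5.2 and 17.3 call underpowered. That limits the weight, though 17.2 does claim power for retention.

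Several stronger readings are tempting, and the documents do not support them:
- A reader might infer that exits without discussion are left to the coder. Section 13.1 fixes their coding.
- A reader might infer that results will drift towards PPJ. Nothing shows this; it is a risk that arises from roles.
- A reader might infer that one or two coding choices decide the retention result. That fits the superseded N of 76 better than the current target.
- A reader might infer that two assistants make masking free. With 25% posts and shared duties, the documents show no spare capacity.

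**Conclusion.** The point holds in limited form. Staff who may attend or lead PPJ groups also record and clean both NUWAY-record outcomes, no step withholds arm, and the 5.4 question does not map onto the definitions in Table 2 and 13.1 (retention) or 5.2 and 20.2 (recurrence). Some judgement therefore remains with people who probably know the arm.

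The size of any bias cannot be derived, because the documents do not say how often a reply would be unclear. At the 17.2 rates with 50 per arm, changing a single exit, one in each arm, or two control exits leaves the retention comparison below .05. Changing two PPJ exits brings it to .054, and two in each arm to .148. These figures assume 1:1 allocation, all participants analysed, and the rates of the earlier behavioural activation study. They show sensitivity, not that miscoding occurs. I could quantify nothing comparable for recurrence. This is a cheap improvement, not a flaw that undermines the pilot.

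**What to change.** 1. In 5.4, replace the question with one identical script for every participant. It should return the recorded exit type (with staff approval, against advice, at staff request, without discussion, or still enrolled) and, separately, each recurrence source: urine, other drug screen, self-report.
2. State one coding rule that joins Table 2 and 13.1, so that no reply needs interpretation.
3. Use a participant list without arm for the look-up. Where scheduling allows, have it done by the assistant who did not attend that cohort's PPJ groups.
4. In 17.4, clean and lock the retention and recurrence variables with the arm field withheld, and merge arm only afterwards.
5. Say in the protocol that masking is partial and that the NUWAY staff who report these outcomes know about PPJ participation.

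The cost is protocol wording and less flexible scheduling of part-time assistants. No extra staff or participant procedures are needed. The change limits bias added by research staff and does not remove bias in what NUWAY reports.
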